11.1 Extent of Exposure

The summary statistics will be produced in accordance with section 9.

11.2 Adverse Events

The summary statistics will be produced in accordance with section 9.”

When calculating the incidence of adverse events, or any sub-classification thereof by treatment, time period, severity, etc., each subject will only be counted once and any repetitions of adverse events will be ignored; the denominator will be the total population size.

Adverse events reported from informed consent until the end of the 30 day follow-up will be reported and analyzed in accordance with section 9.

We will report the AEs that are of interest. The most important AEs are the ones related to the antibiotic treatment, because we expect a difference in the incidence between the usual care group and the PCT-guided treatment group. These AEs include:

- Gastro-intestinal symptoms caused by the antibiotic treatment:
 - o Mainly diarrhea
 - o Clostridium difficile infection
- Allergic reactions to antibiotic treatment

Other AEs of interest are re-admission (all-cause), re-admission (for AECOPD), ICU admission, need for Non-invasive ventilation, death.

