### **Secondary analyses**

The minimal clinically important difference (MCID) of the COPD Assessment Test (CAT) is considered to be a decrease of 2 to 3 points (after rehabilitation) and a decrease of 2 points according to Kon et al. who conducted 3 trials, in patients who underwent rehabilitation, patients who were admitted to the hospital because of an exacerbation and outpatient who were stable (24, 25). We will consider a decrease of 2 points as a minimal clinically important difference. The definition of symptomatic improvement of the E-RS is RS-total  $\geq$  -2.0 (scale range 0-40) (26). Adverse events will be compared by total number of adverse events, of serious adverse events, and separately for gastro-intestinal complaints. Differences in the incidence of these secondary endpoints between randomly allocated strategies will be analyzed by chi-square tests and logistic regression. Secondary endpoints consisting of continuous variables will be analyzed either using the unpaired t-test (for variables with normal distribution) or the Man-Whitney-U test (for variables with a skewed distribution). The distribution will be analyzed when the results are complete.

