5.1 Study Objectives

We hypothesize that at hospitalization for a severe acute exacerbation for COPD, biomarker-guided treatment based on procalcitonin level to guide antibiotic administration is non-inferior to usual care consisting of prednisolone and or antibiotics, which is based on a clinical decision, in terms of treatment failure at day 30.

The secondary objectives are to establish that a biomarker-guided decision algorithm results in an improvement in quality of life, a decrease in consumption of antibiotics, and a reduction of important side effects.

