5.2 Endpoints

The primary objective of this study is to show that at hospitalization for a severe exacerbation of COPD, PCT-guided treatment regarding antibiotic use is non-inferior to usual care consisting of prednisolone and or antibiotics, in terms of treatment failure at day 30 for patients hospitalized because of an acute exacerbation of COPD (AECOPD). Treatment failure is defined as disease-related mortality, endotracheal intubation, vasopressors, renal failure, lung abscess/empyema, pneumonia development or hospital readmission within 30 days after inclusion of the study.

The secondary objectives of this study are to assess the following secondary endpoints:

- Treatment failure defined as an incomplete resolution of the clinical signs and symptoms associated with the AECOPD at day 30 after inclusion of the study (i.e not reaching the baseline condition prior to the AECOPD) scored using the modified Anthonisen criteria.
- Change in Quality of Life on day 1, 10, and after 30 days using the COPD Assessment Test (CAT)
- EXACT – Respiratory symptoms scale (at admission, at day 10 and at day 30 after admission)
- Time to complete resolution of symptoms according to daily symptom diaries evaluating the modified Anthonisen criteria
- Start of antibiotic therapy after an initial opposite decision (after 48 hours)
- Non-Invasive ventilation after 72 hours of admission
- Length of hospitalization
- Re-exacerbation within 30 days
- Side effects (gastro-intestinal complaints, allergic reactions)
- Cumulative antibiotic consumption
- Cumulative prednisolone consumption

6 Study Methods

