 - Test: logistic mixed-effects model.

- Non-Invasive ventilation after 72 hours of admission
 - Dichotomous variable (yes/no)
 - Description: Number and percentage
 - Test: logistic mixed-effects model.

- Length of hospitalization in days
 - Continuous variable, unpaired
 - Description:
 - Normal distribution: mean score \pm SD
 - Skewed distribution: median (IQR)
 - Test: mixed-effects model

- Re-exacerbation within 30 days
 - Dichotomous variable (yes/no)
 - Description: Number and percentage
 - Test: logistic mixed-effects model.

- Side effects (gastro-intestinal complaints, allergic reactions)
 - Nominal/dichotomous variable (yes/no), unpaired
 - Description: Number and percentage
 - Test: logistic mixed-effects model.

- Cumulative antibiotic consumption in days
 - Continuous variable, unpaired
 - Description:
 - Normal distribution: mean score \pm SD
 - Skewed distribution: median (IQR)
 - Test: mixed-effects model

- Cumulative prednisolone consumption in days
 - Continuous variable, unpaired
 - Description:
 - Normal distribution: mean score \pm SD
 - Skewed distribution: median (IQR)
 - Test: mixed-effects model

11 Safety Analyses

All (serious) adverse events reported spontaneously by the subject or observed by the investigator or his staff from the moment of informed consent until the end of the 30 days of follow-up will be recorded. Suspected unexpected serious adverse reactions will also be recorded.

We will list the following (serious) adverse reactions:

- Mortality
 - With a description of the frequencies and percentage in both groups
 - Analysis will be done using Chi square's test or Fisher's exact test, depending on the number of deaths.

- (Serious) adverse reactions
 - With a description of the frequencies and percentage in both groups
 - Analysis will be done using Chi square's test or Fisher's exact test, depending on the number of reactions/events.

Serious adverse events will be summarized as in the table below:

Table 3. Summary of all (serious) adverse events

Outcome measure	Usual care			PCT-guided treatment			(adjusted) odds ratio or relative risk	95% confidence interval	
	n	freq.	%	n	freq.	%		lower limit	upper limit
Mortality									
Adverse effects from antibiotics - Allergic reaction - Diarrhea - Clostridium difficile infection									
Readmission, overall									
Readmission, with AECOPD									
Pneumonia									
ICU-admission									

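### SAP 11.2 and Table 3 compare gastro-intestinal and allergic events by attribution to the antibiotic, while the protocol and the side-effects endpoint set no causality condition

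*SAP*

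**What the plan says.** Two kinds of wording stand side by side.

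**Attributed to the antibiotic**
- SAP 11.2 lists "Gastro-intestinal symptoms caused by the antibiotic treatment" (mainly diarrhoea, and C. difficile infection) and "Allergic reactions to antibiotic treatment". It singles them out "because we expect a difference in the incidence between the usual care group and the PCT-guided treatment group", so a comparison between arms is intended. The denominator is the total population.
- SAP section 11, Table 3, has the row "Adverse effects from antibiotics - Allergic reaction - Diarrhea - Clostridium difficile infection", with columns for an odds ratio or relative risk and a 95% confidence interval.

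**No causality condition**
- Protocol section 10, Secondary analyses: "Adverse events will be compared by total number of adverse events, of serious adverse events, and separately for gastro-intestinal complaints".
- SAP 5.2 defines the secondary endpoint as "Side effects (gastro-intestinal complaints, allergic reactions". SAP 10.2.2 analyses it as yes/no per patient in a logistic mixed-effects model, and Table 2 gives it an odds ratio.
- SAP Tables 5 and 6 list severe diarrhoea, diarrhoea and constipation by arm.
- Protocol 9.2.1 defines an adverse event irrespective of cause. SAP section 11 records all adverse events from consent to day 30.

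The comparison serves a stated secondary objective (SAP 5.1): "a decrease in consumption of antibiotics, and a reduction of important side effects". Neither document says who judges causality or by what rule.

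**The concern.** The two arms are meant to differ in antibiotic use, and an attributed event can occur only in a patient who received an antibiotic. Diarrhoea and gastric complaints also have other causes in acutely ill inpatients who all take prednisolone. In an untreated patient such a complaint drops out of the attributed count. In a treated patient it may be kept, because the person judging it knows that an antibiotic was given. Under protocol 8.2 patients know which treatment they receive. The outcome assessors are blinded to strategy, but causality of adverse events is not among their assigned tasks.

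Background complaints are thus removed more often from the arm with more untreated patients. The resulting contrast partly restates that fewer patients received antibiotics, yet Table 3 would present it as a difference in side effects, with an effect estimate and confidence interval.

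**Working it through.** The documents give no side-effect rate, effect size or power, so there is no figure of the plan's own to reproduce. The check is the size of the artefact.

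**Inputs**
- Antibiotic use in usual care, u1 = 65% (protocol section 1; a national figure, used here as a proxy for the control arm).
- 315 patients per arm (protocol 10.4, SAP 8.5.5).
- Assumed, not in the documents: antibiotic use in the PCT arm u2 = 30–50%; background complaint risk b; risk a added by the antibiotic; fraction f of background complaints in treated patients that is attributed to the drug. The values a, b and f are taken as equal in the two arms.

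**Formulas**
- All-cause risk in an arm: b + u × a. Difference between arms: (u1 − u2) × a.
- Attributed risk in an arm: u × (f × b + a). Difference between arms: (u1 − u2) × (f × b + a).
- Inflation of the risk difference: (f × b + a)/a. Antibiotic use cancels out.

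**Inflation factor**

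| b | a | f = 0 | f = 0.5 | f = 1 |
|---|---|---|---|---|
| 5% | 10% | 1.0 | 1.25 | 1.5 |
| 10% | 10% | 1.0 | 1.5 | 2.0 |
| 15% | 5% | 1.0 | 2.5 | 4.0 |

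**Worked case:** b = 10%, a = 10%, u2 = 40%.
- All-cause: 10% + 0.65 × 10% = 16.5% against 10% + 0.40 × 10% = 14.0%, a difference of 2.5 points (risk ratio 0.85).
- Attributed, f = 0: 6.5% against 4.0%, 2.5 points.
- Attributed, f = 0.5: 0.65 × 15% = 9.75% against 0.40 × 15% = 6.0%, 3.75 points.
- Attributed, f = 1: 0.65 × 20% = 13.0% against 0.40 × 20% = 8.0%, 5.0 points.

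**Ratio scale, which Table 3 uses.** The attributed risk ratio is u2/u1 whatever a, b and f are (if any event is attributed at all): 0.30/0.65 = 0.46, 0.40/0.65 = 0.62, 0.50/0.65 = 0.77. It simply repeats the ratio of antibiotic use.

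**If the antibiotic adds nothing (a = 0).** The all-cause risk ratio is 1.00. The attributed one is still 0.46–0.77 for any f above 0. The chance of a nominally significant reduction (two-sided 0.05, 315 per arm, two-proportion approximation) depends on f × b:

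| f × b | u2 = 50% | u2 = 40% | u2 = 30% |
|---|---|---|---|
| 5% | 8% | 16% | 30% |
| 10% | 13% | 29% | 54% |
| 20% | 22% | 54% | 85% |

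**The case against.** A reader might infer that the SAP counts these events only when the antibiotic caused them, so that the reduction is built into the secondary endpoint. The documents do not support that. Wherever the endpoint is defined or analysed (protocol 8.1.2 and 10.2; SAP 5.2, Table 2 and 10.2.2) it has no causality condition. SAP 11.2 is a list of events of interest within the safety section, and nothing says that it scores the endpoint. Tables 5 and 6 already show diarrhoea by arm without attribution.

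Nor is it right that the PCT arm cannot score. PCT-arm patients with a high value, a later start, or a prescription despite a low value can score. Conversely, about 35% of usual-care patients would be untreated if the national figure applies. The bias comes from the difference in antibiotic use.

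Two further objections stand. Fewer events truly caused by antibiotics, through less exposure, is a real effect of the strategy. And the upper inflation figures assume that every background complaint in a treated patient is blamed on the drug; with perfect attribution the risk difference is not inflated at all.

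These points narrow the concern without removing it:
- Table 3 is itself a planned comparison between arms with an effect estimate, and its row is attributed.
- The term side effects is open to either reading. SAP 11.2 sends adverse events to section 9 for analysis, and section 9 holds Table 2 with the side-effects row, so an analyst could reasonably score that row from 11.2.
- Tables 5 and 6 are only a partial safeguard. Table 6 covers non-serious events above a frequency threshold, and the rows listed in the two tables include neither allergic reactions nor C. difficile infection.

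**Conclusion.** The point holds as an inconsistency that brings a real bias into one planned comparison. SAP 11.2 and Table 3 conflict with protocol section 10 and with SAP 5.2 and 10.2.2. The Table 3 comparison is tilted towards the arm with less antibiotic use. For the side-effects endpoint this is a risk that depends on how it is scored, not an established defect.

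The inflation of the risk difference runs from 1.0 (f = 0) to between 1.5 and 4 (f = 1), for assumed backgrounds of 5–15% and added risks of 5–10%. Only the 65% usual-care figure and the 315 per arm come from the documents; f is unknown, and no causality rule limits it.

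A reader might also infer that the bias feeds the cost analysis, since protocol 8.1.3 and SAP section 13 expect savings from fewer antibiotic side effects. Those sections take resource use from case report forms, hospital systems and a patient questionnaire. Nothing links them to the attributed counts in 11.2 or Table 3, so that inference is not supported.

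The change should be made, because a reduction of side effects is a stated secondary objective.

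**What to change.** 1. In SAP 11.2 and Table 3, count all gastro-intestinal complaints, allergic reactions and C. difficile infections in both arms regardless of attributed cause. Keep the SAP's existing window (consent to day 30) and its existing population for safety outcomes.
2. In SAP 10.2.2, state that the side-effects endpoint is counted in the same way.
3. List antibiotic-attributed events descriptively only, without an odds ratio, and state who judges causality and by what rule.

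The cost is SAP wording. All adverse events are already recorded in both arms, and the schedule assesses them at baseline and on days 3, 5, 10 and 30, so the change to the counts needs no new data.

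The downside is that the difference between arms may be smaller and somewhat noisier. In the worked case above, power at 315 per arm is about 14% for the all-cause comparison, against 54% for the attributed one at f = 1. The higher figure is power to detect a difference of which half is misattributed background, so giving it up is no real loss. The authors should nevertheless expect a wide confidence interval on this endpoint.

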11.3 Deaths, Serious Adverse Events and other Significant Adverse Events

We will report deaths and serious adverse events separate from adverse events. Serious adverse events and other significant adverse events will be reported by organ-system if appropriate.

11.4 Pregnancies (As applicable)

Pregnancy is one of the exclusion criteria of our trial. We do not expect any pregnancies after inclusion, but when there is a suspicion this will be tested. The included population is above 40 years of age which makes a pregnancy less likely to happen during our trial period.

11.5 Clinical Laboratory Evaluations

The summary statistics will be produced in accordance with section 9.

We do not expect difficulties in differences between centers in normal ranges of the most important laboratory evaluations. The PCT concentration has a fixed cut-off, determined by the initiators of the trial. CRP concentration will be reported with a mean value with standard deviations, the normal ranges do not interfere with the type of reporting of this value.

11.6 Prior and Concurrent Medications (As applicable)

Not applicable

11.7 Other Safety Measures

Vital signs will be reported at baseline, these include blood pressure, respiratory frequency, oxygen saturation, heart frequency and body temperature. The summary statistics will be produced in accordance with section 9.

12 Pharmacokinetics (As Applicable)

Not applicable

13 Other Analyses

A cost-effectiveness analysis will be performed led by prof. dr. [name]. The statistics used for this analysis are reported globally below.

Cost-effectiveness analysis (CEA):

- General considerations

Alongside the clinical trial, an economic evaluation will be performed conform the guidelines of the Health Care Institute Netherlands [19]. This evaluation will be conducted from a societal and payer's perspective. When adopting the societal perspective, costs will include 30-day inpatient and outpatient (emergency room, specialist visits) hospital costs, primary care costs (visits to GP and nurse practitioner), medication costs, ambulance costs, productivity costs, informal care costs and travel costs.

- Cost analysis

The resource utilization underlying these costs will be obtained from a combination of sources, including case report forms, hospital administrative systems and a patient's self-reported questionnaire, which is based on an adapted version of the iMTA Medical Consumption Questionnaire (iMCQ) [20]. When adopting the payer's perspective only the costs covered by the Health Insurance Act will be included. Unit costs will be based on reference prices obtained from the costing manual [21]. In a sensitivity analysis we will adjust the unit cost of a hospital day to reflect ward-specific and hospitalization-day-specific costs instead of average costs based on all patients in a hospital. Productivity costs will be based on the Friction Cost method [22]. Savings in health care costs are expected to result from a reduction in antibiotics use, a reduced length of stay and a reduction in the incidence of side-effects from antibiotics. These savings will be compared to the additional costs of adopting the procalcitonin-guided treatment, including the costs of additional lab tests.

- Patient outcome analysis

The difference in total costs between the two groups will be related to the difference in the following outcomes: QALYs, treatment failures and CAT (COPD Assessment Test). This will result in the following incremental cost-effectiveness ratios (ICER): costs per QALY, costs per treatment failure avoided and costs per additional patient with at least one MCID improvement in CAT. The utilities to calculate QALYs will be measured with the EQ-5D-5L with and without the respiratory bolt-on [23]. The ICER's will be estimated using a decision tree model that synthesizes the evidence collected during the clinical trial. The uncertainty around the ICER will be estimated in probabilistic sensitivity analysis, the results of which will be graphically shown in a CE-plane and Cost-Effectiveness Acceptability Curve.

Budget impact analysis (BIA):

- General considerations

A budget impact model to estimate the impact of large-scale implementation of the intervention will be developed. This model will be a transparent cost calculator that includes nation-wide estimates of the size of the COPD population that is hospitalized for exacerbations, scenarios on the proportion and speed of uptake of the procalcitonin-guided AECOPD treatment, and changes in costs as a result of this.

o Cost analysis

These analyses will be conducted in accordance with the ISPOR and Dutch guidelines of ZONMW, for time horizons between 1 and 5 years [24,25].

14 Reporting Conventions

P-values ≥ 0.001 will be reported to 3 decimal places; p-values less than 0.001 will be reported as " <0.001 ". The mean, standard deviation, and any other statistics other than quantiles, will be reported to one decimal place greater than the original data. Quantiles, such as median, or minimum and maximum will use the same number of decimal places as the original data. Estimated parameters, not on the same scale as raw observations (e.g. regression coefficients) will be reported to 3 significant figures.

15 Quality Assurance of Statistical Programming (As Applicable)

The following study-specific documents will be used:

- Study protocol, current version 8, date 19-03-21 (amendment pending version 9, 09-09-21)
- Labmanual, current version 1.0, date 09-03-21
- Informed consent form, current version 1.3, date 26-08-21 (amendment pending version 9, 09-09-21)
- SAE and SUSAR form, current version 1.0, date 28-01-2020


25. ZonMW. Budget Impact Analyses in de praktijk. Leidraad Budget Impact analyse [Internet]. 2020 Feb. Available from: www.facebook.com/zonmwNL

17 Listing of Tables, Listings and Figures

Tables:

- Table 1:
 - Title: Baseline characteristics
 - 3 columns, at least twelve rows
 - Per-protocol population will be given, since this is the primary analysis population
 - Mean will be reported with one decimal, just as the standard deviation and range
 - Median will be reported with one decimal
 - Frequencies will be reported in rounded numbers
 - Percentages will be reported after the frequency as (%) with one decimal
 - Interquartile range will be reported after the median as [IQR] with one decimal

- Table 2:
 - Title: Primary endpoint and secondary endpoints
 - 5 columns, 14 rows
 - Per-protocol population will be given, since this is the primary analysis population
 - Frequencies will be reported in rounded numbers
 - Percentages will be reported after the frequency as (%) with one decimal
 - Interquartile range will be reported after the median as [IQR] with one decimal
 - Adjusted odds ratio/RR/RD will be reported with 2 decimals
 - 95% C.I. will be reported with 2 decimals
 - P-value will be reported with 3 decimals
 - Mean/median value of the CAT and EXACT will be reported with one decimal, just as the standard deviation or the interquartile range[IQR]

- Table 3:
 - Title: Summary of (serious) adverse events
 - 5 main columns, 10 minor columns, number of rows is not known at this point
 - Frequencies will be reported as rounded numbers
 - Percentages will be reported after the frequency as (%) with one decimal
 - The adjusted OR/RR will be reported with 2 decimals
 - 95% C.I. will be reported with 2 decimals

- Table 4:
 - Title: All-Cause Mortality
 - 5 main columns, 10 minor columns, 2 rows
 - Frequencies will be reported as rounded numbers
 - Percentages will be reported after the frequency as (%) with one decimal
 - The adjusted OR/RR will be reported with 2 decimals

- o 95% C.I. will be reported with 2 decimals
- Table 5:
 - o Title: Serious Adverse Events
 - o 5 main columns, 10 minor columns, number of rows is unknown at this moment
 - o Frequencies will be reported as rounded numbers
 - o Percentages will be reported after the frequency as (%) with one decimal
 - o The adjusted OR/RR will be reported with 2 decimals
 - o 95% C.I. will be reported with 2 decimals
- Table 6:
 - o Title: Other (Not Including Serious) Adverse Events
 - o 5 main columns, 10 minor columns, number of rows is unknown at this moment
 - o Frequencies will be reported as rounded numbers
 - o Percentages will be reported after the frequency as (%) with one decimal
 - o The adjusted OR/RR will be reported with 2 decimals
 - o 95% C.I. will be reported with 2 decimals

Figures:

- Figure 1: Consort Flow Diagram
 - o According to the rules of the Consort Flow Diagram
 - Frequencies will be reported as rounded numbers
- Figure 2: Picture of Anthonisen Diary Card
 - o Will not be included in the trial manuscript
